## 5. Retention of Records

The investigator shall retain records required to be maintained under this part for a period of 2 years.

## 6. Data Quality and Monitoring Measures

As much as possible data quality is assessed at the data entry point using intelligent on-line data entry via visual basic designed screen forms. Data element constraints, whether independent range and/or format limitations or 'relative' referential integrity limitations, can be enforced by all methods employed for data input. QA reports assess data quality post-data entry. As we note, data quality begins with the design of the data collection forms and procedures and incorporates reasonable checks to minimize transcription and omission errors. Of the more important quality assurance measures are the internal validity checks for reasonableness and consistency.

- Data Monitoring: The RDCRNDMCC identifies missing or unclear data and generates a data query to the consortium administrator contact.

- **Data Delinquency Tracking:** The Data Management and Coordinating Center will monitor data delinquency on an ongoing basis.

## **7. Registration**

Registration of participants on this protocol will employ an interactive data system in which the clinical site will attest to the participant's eligibility as per protocol criteria and obtain appropriate informed consent. IRB approval for the protocol must be on file at the DMCC before accrual can occur from the clinical site.

The DMCC will use a system of coded identifiers to protect participant confidentiality and safety. Each participant enrolled will be assigned a local identifier by the enrollment site. This number can be a combination of the site identifier (location code) and a serial accession number. Only the registering site will have access to the linkage between this number and the personal identifier of the subject. When the participant is registered to participate in the study, using the DMCC provided web-based registration system, the system will assign a participant ID number. Thus each participant will have two codes: the local one that can be used by the registering site to obtain personal identifiers and a second code assigned by the DMCC. For all data transfers to the DMCC both numbers will be required to uniquely identify the subject. In this fashion, it is possible to protect against data keying errors, digit transposition or other mistakes when identifying a participant for data entry since the numbers should match to properly identify the participant. In this fashion, no personal identifiers would be accessible to the DMCC.

## **8. Data Entry**

Data collection for this study will be accomplished with online electronic case report forms. Using encrypted communication links, on-line forms will be developed that contain the requisite data fields.

## **9. Laboratory Data Flow**

The DMCC will provide laboratories with on-line forms and/or electronic data exchange mechanisms - depending on their capabilities and needs - to enter, update and obtain relevant data. Online forms exist to verify specimen receipt, report specimen issues and submit test results for specimens. The preferred method to exchange data electronically is through the Specimen Management System Web Service. The Web Service allows laboratories to obtain specimen shipment information, receive individual specimens or specimen shipments, report specimen issues and communicate specimen aliquots in a secure manner (test result submission is planned). The DMCC will also support uploading of files electronically. All transactions are logged and validated for both methods.

## **10. Study Completion**

Before a study can be considered completed or terminated, the investigator must have the following data and materials:

- Clinical laboratory findings, clinical data, and all special test results from screening through the EOT visit (to 30 days after the last dose of study agent).
- CRFs properly completed by appropriate study personnel and reviewed and approved by the investigator.
- Copies of protocol amendment(s) and IRB approval/notification if appropriate.
- A summary of the study prepared by the principal investigator (an IRB/IEC summary letter is acceptable).

#### 11. Audits and Inspections

The principal investigator will permit study-related monitoring, audits, IRB review, and regulatory inspections by providing direct access to CRFs and source data/documents.

#### 12. Institutional Review Board Approval

This protocol, the informed consent document, and all relevant supporting data must be submitted to the IRB for approval. IRB approval of the protocol, informed consent document, study materials and any advertisement (if applicable) used to recruit study participants must be obtained before the study may be initiated. This study will utilize a centralized IRB, and the IRB at Cincinnati Children's Hospital Medical Center will serve as the central IRB for the study.

The principal investigator (PI) is responsible for keeping the IRB advised of the progress of the study and of any changes made to the protocol as deemed appropriate, but in any case, at least once a year. The PI is also responsible for notifying the IRB of any unanticipated AEs that occur during the study in accordance with local IRB policies. Recent guidance from the USA FDA suggests that the following AEs should be reported to the IRB/IEC as "unanticipated problems:"

- Any AE that, even without detailed analysis, represents a serious unexpected AE that is rare in the absence of drug exposure (such as agranulocytosis, hepatic necrosis, Stevens-Johnson syndrome).
- A series of AEs that, on analysis, is both unanticipated and a problem for the study. There would be a determination that the series of AEs represents a signal that the AEs were not just isolated occurrences and were significant to the rights and welfare of participants.
- An AE that is described or addressed in the IB/package insert, protocol, or informed consent documents, or is expected to occur in study participants at an anticipated rate (e.g., expected progression of disease, occurrence of events consistent with background rate in participant population), but occurs at a greater frequency or at greater severity than expected.
- Any other AE that would cause the sponsor to modify the investigator brochure, study protocol, or informed consent form, or would prompt other action by the IRB to assure protection of human participants.

It will be the responsibility of the investigator to assure that the essential documents are available at the investigator site. Any or all of these documents may be subject to, and should be available for, audit by CCHMC or Sponsor auditor and inspection by the regulatory authorities as defined in the monitoring plan.

## 17 Publication Policy

The CEGR policy on the publication of study results will apply to this trial. The data generated in this clinical study are the exclusive property of the Sponsor and PI and are confidential. Written approval from the Sponsor is required prior to disclosing any information related to this clinical study. Authorship on the primary publication of the results from this study will be determined by the Sponsor and PI and will be based on contributions to study design, enrollment, data analysis, and interpretation of results.

## 19 Appendices

- 1) 7803 Female Systolic Blood Pressures Age 5 - 17 Years
- 2) 7803 Female Diastolic Blood Pressures Age 5 - 17 Years
- 3) 7803 Male Systolic Blood Pressures Age 5 - 17 Years
- 4) 7803 Male Diastolic Blood Pressures Age 5 - 17 Years
- 5) 7803 Adult Blood Pressures  $\leq 18$  Years

NIH Approved 12/06/18

### 19.1 Systolic Blood Pressures for Females Age 5 – 17 Years (Updated)

Gender	Age (Y)	Age (M)	BP Percentile	Systolic Height Percentile								
				1st	2nd	5th	10th	25th	50 th	75th	90th	95th
Female	5	60	2	68	69	70	71	72	74	75	77	78
Female	6	72	2	70	70	71	72	74	75	77	78	79
Female	7	84	2	71	71	72	73	75	76	78	79	80
Female	8	96	2	71	72	73	74	75	77	79	81	82
Female	9	108	2	71	72	73	74	76	79	81	83	84
Female	10	120	2	73	74	75	76	78	81	83	85	86
Female	11	132	2	75	76	78	79	81	84	85	86	86
Female	12	144	2	79	80	81	83	85	86	86	86	86
Female	13	156	2	82	83	84	85	86	87	87	87	88
Female	14	168	2	84	85	86	86	87	87	88	89	89
Female	15	180	2	85	85	86	87	88	88	89	90	90
Female	16	192	2	86	86	87	88	89	90	91	91	91
Female	17	204	2	87	87	88	89	91	91	92	92	93

### 19.2 Diastolic Blood Pressures for Females Age 5 – 17 Years (Updated)

Gender	Age (Y)	Age (M)	BP Percentile	Diastolic Height Percentile								
				1st	2nd	5th	10th	25th	50 th	75th	90th	95th
Female	5	60	2	31	31	31	32	32	33	33	34	34
Female	6	72	2	31	31	32	32	32	33	33	33	33
Female	7	84	2	31	31	31	31	31	32	32	32	33
Female	8	96	2	29	30	30	30	31	32	34	35	36
Female	9	108	2	31	32	32	33	33	34	35	36	37
Female	10	120	2	32	33	33	33	34	35	35	36	37
Female	11	132	2	33	33	33	33	34	34	35	37	38
Female	12	144	2	33	33	33	33	34	35	36	37	37
Female	13	156	2	35	35	35	35	36	36	37	37	37
Female	14	168	2	39	39	39	39	39	40	41	42	43
Female	15	180	2	43	43	43	43	43	45	46	47	47
Female	16	192	2	44	44	44	43	44	46	48	48	49
Female	17	204	2	44	44	43	42	44	47	48	48	48

### 19.3 Systolic Blood Pressures for Males Age 5 – 17 Years (Updated)

Gender	Age (Y)	Age (M)	BP Percentile	Systolic Height Percentile								
				1st	2nd	5th	10th	25th	50th	75th	90th	95th
Male	5	60	2	70	71	71	72	73	75	76	77	78
Male	6	72	2	71	72	73	74	75	76	77	78	79
Male	7	84	2	72	73	74	75	76	77	78	80	80
Male	8	96	2	73	74	75	76	77	79	80	81	82
Male	9	108	2	75	76	77	78	79	81	82	83	84
Male	10	120	2	77	78	79	80	81	83	84	85	85
Male	11	132	2	79	80	81	82	83	84	85	86	87
Male	12	144	2	81	82	83	83	85	86	87	88	89
Male	13	156	2	83	83	84	85	86	87	89	90	91
Male	14	168	2	83	84	84	85	87	89	91	92	92
Male	15	180	2	84	84	85	87	89	91	92	93	94
Male	16	192	2	86	87	88	90	92	94	94	95	95
Male	17	204	2	88	89	91	93	95	96	97	97	98

### 19.4 Diastolic Blood Pressures for Males Age 5 – 17 Years (Updated)

Gender	Age (Y)	Age (M)	BP Percentile	Diastolic Height Percentile								
				1st	2nd	5th	10th	25th	50th	75th	90th	95th
Male	5	60	2	28	28	29	29	30	31	32	33	33
Male	6	72	2	30	30	31	31	32	33	34	34	34
Male	7	84	2	31	31	31	32	32	33	34	34	34
Male	8	96	2	30	30	31	31	32	33	34	35	36
Male	9	108	2	29	30	31	31	33	35	36	37	38
Male	10	120	2	30	30	32	33	34	36	38	39	40
Male	11	132	2	30	31	32	33	35	36	38	38	38
Male	12	144	2	30	31	32	33	34	36	36	36	35
Male	13	156	2	31	31	32	33	34	34	34	34	34
Male	14	168	2	33	33	34	34	35	35	36	37	38
Male	15	180	2	34	35	36	36	37	39	40	41	42
Male	16	192	2	36	37	38	39	41	42	43	44	44
Male	17	204	2	38	39	40	41	43	44	45	46	46

**19.5 Adult Blood Pressures for Males and Females  $\geq 18$  Years**

	Systolic and Diastolic Blood Pressure 5th Percentile	
	Systolic Min	Diastolic Min
Female	105	60
Male	105	60

NIH Approved 12/06/18

**A Preliminary Open-Label Trial of Losartan Potassium in
Participants with Eosinophilic Esophagitis (EoE) With or
Without a Connective Tissue Disorder (CTD)**

SAP Date: 12/11/2019

NCT03029091

Statistical Analysis Plan

CCHMC

A Preliminary Open-Label Trial of Losartan Potassium in Participants with Eosinophilic Esophagitis (EoE) With or Without a Connective Tissue Disorder (CTD)

Principal Investigator: [REDACTED]

Statisticians: [REDACTED]

Project Sponsor: NCATS, NIDDK, NIAID

Grant Number (if applicable):

CCHMC IRB Number: 2015-9021

IRB Approval Date(s): 5/4/2020 (last continuing review)

Purpose of Study

The primary objective of this proposal is to assess the effect of losartan on the reduction of esophageal eosinophils in participants with eosinophilic esophagitis (EoE) with or without a connective tissue disorder (CTD). Participants aged 5 to 25 years with active EoE will be enrolled and the primary efficacy outcome will be the change in esophageal eosinophil number obtained following a 16-week trial of Losartan. During the screening process, active EoE will be confirmed by research pathologist review (histologic evaluation) of esophageal biopsies obtained during by esophagogastroduodenoscopy (EGD) in subjects with a history consistent with EoE.

Hypotheses

Inhibition of the TGF- β 1 pathway could provide a unique means of improving patient care in EoE via the reduction in smooth muscle contraction mediated by the deep-lying mast cells and TGF- β 1, as well as reducing pathologic fibrosis and cellular proliferation seen in these patients. Herein we propose that a reduction in TGF- β 1 activity via losartan in patients with EoE will lead to reduced eosinophilia, fibrosis, and smooth muscle contractility, which each play a role in the pathogenesis and symptomatology of this disease. Further, the use of a once-a-day oral medication, without the difficulties associated with either steroid medications or dietary modification, could provide improved compliance and quality of life for this

patient population. This represents a preliminary descriptive study in which the impact of losartan therapy in patients with EoE or EoE-CTD is assessed.

[figure not shown]
Primary Objective(s)

The primary objective of this open-label pilot study is to assess the effect of losartan on the reduction of esophageal eosinophils in participants with EoE with or without a CTD.

Study design

This is a phase II, open-label trial of losartan in patients diagnosed with EoE with or without a CTD. Prior to entry, patients must meet the current consensus criteria for EoE in which efforts are made to rule out other causes of esophageal eosinophilia. The trial will perform a preliminary assessment of the effect of the maximum tolerated dose of losartan in participants with active EoE as determined by the absence of side effects and by vital signs being within normal limits. The primary endpoint of the study is the reduction in the number of esophageal eosinophils in participants who will receive losartan orally once a day (Figure 1). The primary safety endpoint is descriptive and will require reporting of SAE or Grade 3 and above AEs.

Figure 1 Study Design Flowchart

Analysis Populations

The analysis population for the primary and secondary endpoints will be participants who received Losartan and maintained the baseline EoE treatment throughout the course of the study.

Statistical Considerations and Analytical Plan

Overview

Change from baseline for eosinophil counts will be calculated for each participant. The average change from baseline within each group and combining both groups (i.e. EoE and EoE-CTD) will be calculated along with the corresponding two-sided, 95% confidence interval. Additionally, we will perform paired tests which will specifically test whether there was significant change between baseline and study completion. The last observation carried forward (LOCF) method will be used for participants who end the trial early. To assess changes over time for continuous secondary and safety outcomes, a mixed effects model for repeated measures analysis will be used. Unless stated otherwise, all statistical testing will be done at $\alpha=0.05$.

Variables of Interest

Primary outcome:

- 1) Change in eosinophils/hpf from baseline to post treatment
- 2) Rate of SAE / Grade 3 or above AE

Secondary outcomes:

- 1) Blood (serum) and esophageal TGF- β levels
- 2) EoE transcriptome
- 3) Histopathology as assessed by the Histology Scoring System (HSS): Will include the overall score, grade score, stage score, and the inflammatory and structural sub-scores. Scores will be reported as distal, proximal, and maximum
- 4) Esophageal compliance as measured by EndoFLIP.
- 5) PROS (Pediatric Eosinophilic Esophagitis Symptom Severity [PEESS], PedsQL Eosinophilic Esophagitis Module [PedsQLTM EoE], EoE Quality of Life Questionnaire, and EEsAI)

Derived Variables.

- 1) HSS scores. Sum of the feature scores divided by the maximum possible score for the biopsy for grade and stage. The HSS assesses eight histological features: eosinophilic inflammation, basal zone hyperplasia, eosinophilic abscess, eosinophilic surface layering, dilated intercellular spaces, surface epithelial alteration, dyskeratotic epithelial cells, and lamina propria fibres. Each feature is scored on a 4-point scale for severity (grade) or extent (stage) of the abnormality, with 0 representing normal features and 3 denoting most severe or extensive features. A final HSS score (grade or stage) is the sum of the assigned scores for each feature assessed divided by the maximum possible score for that biopsy specimen;⁷ we defined the HSS total score as the sum of the HSS final scores for grade and stage. Therefore, the HSS total score ranges from 0 to 2 because each

HSS final score ranges from 0 to 1. Inflammatory sub-scores include the following features: eosinophils, abscesses, surface layering, and surface necrosis. Structural sub-scores include basal layer hyperplasia, dilated intercellular spaces, apoptotic epithelia, and lamina propria fibrosis.

- 2) EndoFLIP –
- 3) EREFS. In EREFS, five endoscopic features are scored for both the distal and proximal or mid-oesophagus: oedema (0–1), rings (0–3), exudates (0–2), furrows (0–2), and strictures (0–1). We will calculate the EREFS total score by adding the assigned scores for each feature in both the distal and proximal or mid-oesophagus; the EREFS total score ranges from 0 to 18.
- 4) Adherence. Adherence will be dichotomized into mostly adherent vs not-mostly adherent based on the number of missed doses. The statistician will provide descriptive data to one of the study clinicians to determine what is the appropriate threshold for non-adherence. Once a threshold has been selected, the statistician will provide an adherence classification on each participant.
- 5) Atopy. Atopy is a multi-faceted disease. Individuals will be defined as atopic if they report a history of asthma, eczema, allergic rhinitis, allergic conjunctivitis, IgE mediating food allergy and/or atopic dermatitis.
- 6) Time since diagnosis will be calculated as the study date at baseline minus the date at diagnosis.

Prior to any hypothesis testing, all variables will be reviewed for plausibility. Any values which are considered suspect will be reviewed by the clinical team to ensure accuracy. Continuous data will be evaluated for distributional assumptions of normality. Natural log-transformation will be considered for right skewed non-normally distributed data (the most typical skew seen in physiologic data).

Demographics/Patients Characteristics

Demographic, patient characteristics, medication use, and study completion status will be summarized using median [interquartile range] for continuous variables and frequency and percentages for categorical variables. Treatment comparisons will be performed for demographics and patient characteristics using the Wilcoxon Rank sum test for continuous variables and the Fisher's Exact test for categorical variables. All tests will be conducted at $\alpha=0.05$.

Analysis of Primary Outcome

Primary Objective:

1. To assess the effect of losartan on the reduction of esophageal eosinophils in participants with EoE with or without a CTD.

Change from baseline for eosinophil counts will be calculated for each participant. The average change from baseline within each group and combining both groups (i.e. EoE and EoE-CTD) will be calculated

along with the corresponding two-sided, 95% confidence intervals. If the assumption of normality is not viable for the change from baseline score, we will use a square root transformation on the eosinophil counts prior to calculating the change from baseline and determine if the “change score” attains normality. If this transformation is not successful, the median of the change will be calculated along with the 95% confidence interval for the median using Hodges-Lehmann estimators. Each confidence interval will be visually inspected to determine if zero is a possible value for the true change from baseline (μ). This corresponds to testing the following hypothesis:

H0: $\mu=0$ vs. H1: $\mu\neq 0$.

The last observation carried forward (LOCF) method will be used for participants who end the trial early.

Additionally, to evaluate the effect of losartan on the reduction of esophageal eosinophils in participants with EoE (with or without a CTD), we will use paired non-parametric Wilcoxon Rank sum test. The Wilcoxon rank sum paired test will be used given the small sample size and the broad range of eosinophils which could be present in our participants. Analyses will be performed using the whole cohort and stratified by CTD. Statistical significance will be set at $\alpha = 0.05$. This corresponds to testing the following hypothesis:

H0: baseline and study completion are equal vs. H1: baseline and study completion are not equal.

Analyses of Secondary Endpoint(s)/Outcome(s)

To assess changes over time for continuous secondary and safety outcomes, a mixed effects model for repeated measures analysis will be used. The dependent variable will be the change from baseline. The “participant nested within group” term will be considered a random effect. Time (i.e. measurement time) will be included as a continuous effect. Terms in the model will be time, group (i.e., EoE and EoE-CTD), and time-by-group interaction. The baseline value will be used as a covariate in the model. If necessary, to meet the assumptions of the analysis, an appropriate transformation will be used (e.g., square root, log, rank). The hypotheses that will be tested are whether there is a significant trend over time and whether this trend is consistent between the CTD and non-CTD groups (i.e. testing the interaction term). If the trend is not consistent between groups based on the statistical test at $\alpha=0.10$, we will estimate the trend within each of the two groups by including terms in the statistical model that estimates the trend within each group and the hypothesis to be tested within each group is whether this trend is significantly different than zero. We will systematically assess the residuals to determine whether a linear or quadratic model best fits the data. In statistical terms, the hypotheses are provided below.

For testing consistency of the time trend (β) between the CTD and non-CTD group, the hypotheses are:

H0: $\beta_{\text{EoE-CTD}} = \beta_{\text{EoE (non-CTD)}}$ vs. H1: $\beta_{\text{EoE-CTD}} \neq \beta_{\text{EoE (non-CTD)}}$.

For testing linear trend combining across groups (if there is consistency of the time trend):

H0: $\beta=0$ vs. H1: $\beta\neq 0$ where β is the slope of the line across groups. Similar hypotheses will be tested if analysis of the residuals indicates that higher order terms need to be included in the model (e.g. quadratic). If there is strong evidence that the time trend is not consistent between the two groups, we will test the above hypothesis within each of the two groups. In addition, the two-sided, 95% confidence interval for the slopes will be calculated to provide estimates of the slope for future studies.

The percentage of participants for whom peak eosinophil counts are < 15 eosinophil/HPF at Week 16 will be estimated within each CTD group along with a 95% confidence interval.

Safety endpoints that are categorical will be summarized within each group. Further, any SAEs or Grade 3 or above will be reported descriptively.

Software Used (with References) and Specialized Macros (with References)

SAS version 9.4, JMP 14.

This SAP has been reviewed and approved by:

Investigator

Date

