### 3. Primary Endpoint(s)/Outcome(s)

- Change from baseline in the peak esophageal eosinophil count in participants receiving losartan potassium at the end-of-treatment (EOT) visit (or at early withdrawal) as determined by esophagogastroduodenoscopy (EGD) with biopsy and reported as eosinophils per high-power field (eosinophils/HPF).
- A primary safety endpoint is also included to monitor for adverse events in the enrolled subjects. Specifically, as a descriptive investigation, any SAE or Grade 3 and above AEs that arise during the conduct of this pilot study will be reported.

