### 3. Participant Replacement

Enrolled participants who receive the study agent and prematurely discontinued or withdraw from the study will be replaced if they do not reach Week 16 of the study, including the EOT visit (EGD). Additional participants will be enrolled in the same manner as all other participants. Participant numbers will not be re-used. Any enrolled participant will be included in the intent-to-treat analysis.

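### The SAP analyses only participants who kept their baseline EoE therapy, although the protocol promises an intent-to-treat analysis; this can drop some treatment failures and leaves the SAE/Grade 3+ denominator unclear

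*SAP*

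**What the plan says.** **Efficacy population.** The SAP, under Analysis Populations, has one definition: "The analysis population for the primary and secondary endpoints will be participants who received Losartan and maintained the baseline EoE treatment", with the condition covering the whole study. It names no intent-to-treat, per-protocol or safety set and gives no reason for differing from the protocol. Protocol section 10.3 says: "Any enrolled participant will be included in the intent-to-treat analysis". The same section replaces participants who take the drug and stop before the Week 16 endoscopy (EGD), so the number treated can exceed 15.

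**Response rate.** In the SAP's secondary analyses, the percentage with a peak count below 15 eosinophils/HPF "at Week 16 will be estimated within each CTD group along with a 95% confidence interval". It is in neither document's list of outcomes.

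**Safety.** Protocol section 3.3 says: "A primary safety endpoint is also included to monitor for adverse events in the enrolled subjects". The SAP lists "Rate of SAE / Grade 3 or above AE" as its second primary outcome, with no denominator. It also says "The primary safety endpoint is descriptive and will require reporting of SAE or Grade 3 and above AEs" (Study design) and "Further, any SAEs or Grade 3 or above will be reported descriptively" (end of the secondary analyses).

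**The concern.** Both population statements are current text, and an analyst cannot follow both. The SAP's condition depends on what happens after treatment starts, and that is tied to outcome. Protocol section 6.5 describes insufficient effect as the need for alternative or added EoE treatment, including rescue corticosteroid. A change of EoE therapy is therefore one form that failure takes, and the SAP excludes on it.

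The rule also lacks an end date and a definition of a change. Inclusion criterion 5 (section 4.2) counts diet as baseline therapy. Small dietary modifications, which section 6.5 says are not grounds for withdrawal, could therefore exclude someone.

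With 15 participants, one or two exclusions move a percentage visibly. Protocol section 12.5 says that the effect estimates will be used to power later studies, so a selected rate would carry forward.

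**Working it through.** **1. How a failure leaves the set.** Section 6.5 allows study drug to be stopped when other EoE therapy is needed. Sections 8.8 and 10.4 then call for an EGD at withdrawal. Section 8.8 allows one week from the last dose, and a footnote to Table 4 allows two; these should be reconciled. Someone biopsied before new therapy starts can stay in the SAP set. Someone who starts new therapy first does not. So the rule can drop some failures, mainly those who change therapy before the EGD.

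**2. The plan's own figures.** Table 7, N = 15, SD 5 on the square-root scale: half-width = t(0.975, 14) × SD/√n = 2.145 × 5/√15 = 2.77, as stated (±2.8). Table 8 uses the score interval, [p + z²/2n ± z√(p(1−p)/n + z²/4n²)] / (1 + z²/n). This reproduces 17 of its 18 limits. The exception is N = 15 at 40%: the table gives 28% to 64%, the formula 19.8% to 64.3%. That is a separate matter; I use the formula.

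**3. Response rate.** Inputs: 15 participants (section 12.5) and a 40% response, one of the rates in Table 8, so 6/15. The number dropped, k = 1 to 4, is my assumption; the documents give no rate of therapy change.

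| Case | k = 1 | k = 2 | k = 3 | k = 4 |
|---|---|---|---|---|
| Failures dropped, not replaced: SAP reports 6/(15−k); true 40% | 42.9% | 46.2% | 50.0% | 54.5% |
| Failures dropped and replaced: SAP reports 6/15 = 40%; all treated 6/(15+k) | 37.5% | 35.3% | 33.3% | 31.6% |
| Responders with minor changes dropped: SAP reports (6−k)/(15−k); true 40% | 35.7% | 30.8% | 25.0% | 18.2% |

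The first row is for people who change therapy but reach Week 16. The second is for those who leave early after changing therapy before any withdrawal EGD. The 95% score intervals are 21.4% to 67.4% for 6/14 and 28.0% to 78.7% for 6/11. In the EoE-CTD group, one dropped failure turns a true 2/5 = 40% into 2/4 = 50%; if that person is replaced, 2/5 is shown where all treated give 2/6 = 33.3%.

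**4. Mean change.** If the window ends at the EGD, the set loses only those who changed therapy before it. Restoring k of 15 moves the mean by (k/15) × (mean of dropped − mean of kept). As a limiting case, assume the kept average −3 on the square-root scale and the dropped enter at zero. The all-dosed mean is then −3 × (15−k)/15 = −2.80, −2.60, −2.40 or −2.20 for k = 1 to 4. That is a shift of 0.2 to 0.8, against a planned half-width of 2.8. Dropped participants whose biopsies resemble the rest cause no shift.

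**5. Safety rate.** Suppose one event falls in an excluded participant. Without replacement and with one person excluded, the SAP set gives 0/14 (exact upper limit 23.2%) and all dosed give 1/15 = 6.7% (0.2% to 31.9%). With replacement, it is 0/15 (upper limit 21.8%) against 1/16 = 6.3%.

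**The case against.** **Stable background therapy is a legitimate design condition** (section 4.2 criterion 5; section 7.1), and the withdrawal EGD protects many failures from exclusion. Both points stand. They make the SAP set reasonable as a supportive analysis and the route for losing failures narrow. They do not reconcile it with section 10.3.

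**LOCF shows that the SAP means to keep early leavers.** Entry requires at least 15 eosinophils/HPF, so a leaver with no later EGD would already count as a non-responder if LOCF were applied to the response rate. This stands for leavers who kept their therapy. It does not help those whom the population rule removes before LOCF applies.

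**The safety point is thin.** The SAP's Study design section separates the primary endpoint from the primary safety endpoint, so the population sentence may be meant for efficacy only. A reader might infer that serious events in excluded participants would go unreported. The documents do not support that: the SAP has all SAEs and Grade 3+ events reported descriptively. Only the denominator is unsettled.

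**The trial is a small descriptive pilot, and k has no source.** True. The shifts shown sit inside intervals more than 40 percentage points wide. That limits the size of the point, not the textual conflict.

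**Conclusion.** The conflict is explicit, and the SAP rule can select on outcome. It should be fixed, although it does not undermine the trial. The main effect is on the descriptive rate below 15 eosinophils/HPF: 40% reported as 42.9% to 54.5%, or 40% shown where all treated give 37.5% to 31.6%, for an assumed 1 to 4 failures dropped.

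Two stronger conclusions are tempting but not supported:

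- **That the rule must favour losartan.** It can equally drop responders with small dietary changes, so the direction is open and the actual size cannot be derived.
- **That mean change is materially inflated because the window runs to the Week 20 follow-up**, where diet and medication are checked again (section 8.9). The SAP describes a 16-week trial and tests eosinophils from baseline to study completion, and the only scheduled post-baseline EGD is at end of treatment or withdrawal. The natural window ends there. Mean change is then little affected, provided that few participants change therapy before the EGD.

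For safety, the finding is an unclear denominator and nothing more.

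**What to change.** 1. **Main efficacy set.** Amend protocol section 10.3 and the SAP's Analysis Populations to the same definition: everyone who received at least one dose, including those later replaced. Show any enrolled but never dosed in the flow table.
2. **Response rate.** Count as non-responders those with no end-of-treatment or withdrawal EGD and those who began new or additional EoE therapy before it. Exclude no one for a change made after the EGD.
3. **Mean change.** Include every dosed participant. Use the end-of-treatment or withdrawal EGD where one exists, whether or not therapy changed, and keep the stated LOCF rule for those with none. Report how many values are carried forward; each enters as zero change, because the only other scheduled EGD is the screening one. Show the result without them as a sensitivity analysis. Limiting the main analysis to biopsies taken before a therapy change would make it complete-case and move it further from section 10.3.
4. **Supportive analysis.** Keep the present SAP set, labelled as such, with its window ending at the end-of-treatment or withdrawal EGD. List by participant any start, stop or dose change of swallowed steroid, PPI or diet therapy.
5. **Safety.** State that the SAE/Grade 3+ rate uses everyone who received at least one dose.

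The cost is wording changes in both documents and one extra table, with no new data. The response rate may come out slightly less favourable.
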